6.1	Medical previous history	54
6.2	Physical examinations	54
6.3	Hematology	55
6.4	Blood chemistry	55
6.5	Immunochemistry	55
6.6	Bone marrow assessment	56
6.7	Specific additional investigations	56
7	SAFETY ASSESSMENT	56
7.1	Adverse Events Reporting	57
7.2	Serious Adverse Events	58
7.3	SUSAR reporting	60
7.4	Pregnancy	62
7.5	Overdose	63
7.6	Potential Drug-Induced Liver Injury (DILI)	63
7.7	Other Safety Considerations	64
8	DATA MONITORING COMMITTEE	65
8.1	Data and documents handling	65
8.2	Amendments	65
9	STATISTICAL CONSIDERATIONS	65
9.1	Endpoint Definitions	66
9.2	Statistical and Efficacy Analyses	66
9.3.	Demographics and Baseline Characteristics	67
10	STUDY MANAGEMENT	68
10.1	Compliance with the Protocol	68
10.2	Publication	68
10.3	Destruction of investigational products	68
	APPENDIX 1 ECOG SCALE	69
	APPENDIX 2 COCKCROFT-GAULT EQUATION	69
	APPENDIX 3 NYHA CLASSIFICATION	70
	APPENDIX 4 ISS STAGE	70
	APPENDIX 5 IMWG CRITERIA	71
	APPENDIX 6 ELOTUZUMAB ADMINISTRATION GUIDELINES	74
	APPENDIX 7 CIOMS FORM	77
	REFERENCES	78

Principal Investigator signature page

Signature of Investigator

Printed name of Investigator

Date

LOCAL INVESTIGATOR SIGNATURE

Local site name: _____

Local Investigator: _____
Signature of Investigator

Printed name of Investigator

Date

By my signature, I agree to personally supervise the conduct of this study and to ensure its conduct in compliance with the protocol, informed consent, IRB/EC procedures, the Declaration of Helsinki, ICH Good Clinical Practices guideline, the EU directive Good Clinical Practice, and local regulations governing the conduct of clinical studies.

Study Title: Phase 2 study carfilzomib + elotuzumab + dexamethasone for relapsed or progressed multiple myeloma patients after 1-3 prior treatment lines

Phase: Phase 2

Number of Patients: 40

Study Objective: To investigate the safety and feasibility of carfilzomib + elotuzumab + dexamethasone combination and initial efficacy in relapsed or progressed multiple myeloma patients

Study Endpoints

Primary

- Overall response rate (ORR) with carfilzomib + elotuzumab + dexamethasone

Secondary

Complete response rate (CR)

- Quality of response (proportion of minimal residual disease (MRD) negativity in patients with at least VGPR response)
- Duration of responses
- Progression-free survival (PFS)
- Time to next treatment (TTNT)
- Safety (Adverse events)

Overview of Study Design:

This Nordic Myeloma Study Group study is a phase 2 study for advanced MM patients below 75 years of age. The main aim of this study is to assess the ORR with a new drug combination, carfilzomib + elotuzumab + dexamethasone (CAR-ELO-Dex). Even if this is not a randomized study rough comparisons can be done with earlier reports of different regimens in the same clinical situation. In addition, safety assessment is of critical importance for a new regimen. A modern concept is to study the depth of CR responses with a sensitive multiparameter flow cytometry (MFC) method for MRD assessment – an endpoint that is mostly lacking in previous studies for this patient population. We assume that treatment with this new combination of CAR + ELO + Dex will produce at least as good responses as the most efficient regimens so far used in this clinical situation, and there will be a substantial proportion of CR responses with MRD-negativity which can be regarded as an indicator of high-level treatment efficacy and which gives a good basis for comparisons of treatment efficacy between different study regimens in future.

The target population of the study is the patients who have relapsed or progressed after 1 to 3 prior treatment lines in which PI (bortezomib and/or ixazomib) and/or lenalidomide have

Helsinki University Hospital Comprehensive Cancer Center Hematology
Clinical study protocol NMSG#24/15

been included. The primary endpoint is overall response rate (ORR) while the secondary endpoints include complete remission (CR), duration of response, assessment of the depth (quality) of CR with MRD measurement by flow cytometry, estimation of PFS and time to next treatment, and evaluation of adverse events and safety.

The cycle length is 28 days.

The ELO dose is 10 mg/kg in all cycles.

CAR dose is initially (Cycle 1, day 1) 20 mg/m² weekly after which it will be increased to 56 mg/m² weekly in the first 5 patients in the first two cycles. If no safety problems occur the dose is increased to 70 mg/m² weekly for the rest of the study, and the patients after the first 5 patients will receive this dose right after the initial weekly dose of 20 mg/m²

Dexamethasone dose is 40 mg weekly throughout the study.

Drug administration schedule:

Cycles 1-2

CAR and ELO are administrated at weekly intervals on cycle days 1, 8 and 15.

Dexamethasone will be given on days 1, 8, 15 and 22.

Cycles 3-8

CAR will be administered similarly as in cycles 1-2.

ELO will be given on cycle days 1 and 15.

Dexamethasone as in cycles 1-2.

Cycles 9 -

CAR, ELO and Dex will be given on days 1 and 15 from cycle 9 until relapse or progression or excess toxicity.

Duration of Study:

Expected duration of treatment:

- patient recruitment 24 months
- primary endpoint (ORR) together with the relevant secondary endpoints will be assessed after the minimum follow-up of one year has been reached with the last included patient
- to assess PFS and TTNT all patients will be followed until 4 years after first dose

Helsinki University Hospital Comprehensive Cancer Center Hematology
Clinical study protocol NMSG#24/15

LIST OF ABBREVIATIONS AND GLOSSARY OF TERMS

Common abbreviations used in oncology protocols are provided below. Program-specific or protocol-specific abbreviations must be added to this list, and unnecessary abbreviations removed, as applicable. Abbreviations that are retained should not be changed.

Abbreviation	Term
AE	adverse event
AFOS	alkaline phosphatase
ALT, ALAT	alanine aminotransferase
ANC	absolute neutrophil count
API	active pharmaceutical ingredient
ASCO	American Society of Clinical Oncology
ASCT	Autologous stem cell transplantation
ASO-RQ	Allele specific oligonucleotide real-time quantification
AST	aspartate aminotransferase
AUC	area under the plasma concentration versus time curve
AUC _{24 hr}	area under the plasma concentration versus time curve from zero to 24 hours
AUC _{inf}	area under the plasma concentration versus time curve from zero to infinity
AUC _τ	area under the plasma concentration versus time curve from zero to next dose
BID	bis in die; twice a day
BM	bone marrow
BSA	body surface area
BUN	blood urea nitrogen
BZM	Bortezomib
CBC	complete blood count
CL	clearance, IV dosing
CL _p	plasma clearance
CL _{Total}	total clearance
C _{max}	single-dose maximum (peak) concentration
CNS	central nervous system
CR	complete remission
CrCl	Creatinine Clearance
CRO	Clinical trial research organization
CRP	C-reactive protein
CT	computed tomography

Helsinki University Hospital Comprehensive Cancer Center Hematology
Clinical study protocol NMSG#24/15

Abbreviation	Term
CY	Cyclophosphamide
CYP	cytochrome P ₄₅₀
DDI	drug-drug interaction
DLT	dose-limiting toxicity
DME	drug metabolizing enzymes
DNA	deoxyribonucleic acid
DSRT	Drug sensitivity and resistance testing
ECG	Electrocardiogram
ECOG	Eastern Cooperative Oncology Group
eCRF	electronic case report form
ELISA	enzyme-linked immunosorbent assay
EU	European Union
FDA	United States Food and Drug Administration
FISH	Fluorescence in situ hybridization
GCP	Good Clinical Practice
G-CSF	granulocyte colony stimulating factor
GFR	Glomerular filtration rate
GI	Gastrointestinal
GLP	Good Laboratory Practices
GMP	Good Manufacturing Practice
Hb	Hemoglobin
Hct	Hematocrit
HDT	High-dose treatment
HIV	human immunodeficiency virus
HR	High-risk
IB	Investigator's Brochure
IC ₅₀	concentration producing 50% inhibition
ICF	informed consent form
ICH	International Conference on Harmonisation
IEC	independent ethics committee
IMiD	Immunomodulatory drug
IMWG	International Myeloma Working Group
IRB	institutional review board

Helsinki University Hospital Comprehensive Cancer Center Hematology
Clinical study protocol NMSG#24/15

Abbreviation	Term
ITT	intent-to-treat
IV	intravenous; intravenously
KPS	Karnofsky Performance Status
LDH, LD	lactate dehydrogenase
LR	Low-risk
MDS	Myelodysplasia
MedDRA	Medical Dictionary for Regulatory Activities
MFC	Multiparameter flow cytometry
Millennium	Millennium Pharmaceuticals, Inc., and its affiliates
MM	Multiple myeloma
MR	Minimal response
MRI	magnetic resonance imaging
MRD	Minimal residual disease
MTD	maximum tolerated dose
NCI	National Cancer Institute
NCI CTCAE	National Cancer Institute Common Terminology Criteria for Adverse Events
NDMM	Newly diagnosed multiple myeloma
NGS	Next generation sequencing
NMSG	Nordic Myeloma Study Group
nCR	Near complete remission
NYHA	New York Heart Association
ORR	Overall response rate
OS	Overall survival
PCR	polymerase chain reaction
PD	Progressive disease
PFS	Progression-free survival
PB	Peripheral blood
Pgp	P-glycoprotein
PI	Proteasome inhibitor
PK	pharmacokinetic(s)
PO	per os ; by mouth (orally)
PR	partial remission
PRO	patient-reported outcome

Helsinki University Hospital Comprehensive Cancer Center Hematology
Clinical study protocol NMSG#24/15

Abbreviation	Term
QD	quaque die ; each day; once daily
QID	quater in die ; 4 times a day
QOD	quaque altera die ; every other day
QOL	quality of life
RNA	Ribonucleic acid
RRMM	Relapsed/refractory multiple myeloma
SAE	serious adverse event
SC	Subcutaneous
sCR	Stringent complete remission
SD	stable disease
SJS	Stevens-Johnson syndrome
SmPC	Summary of Product Characteristics
SPM	Second primary malignancy
SR	Standard-risk
$t_{1/2}$	terminal disposition half-life
TEN	Toxic epidermal necrolysis
TFR	Tumor flare reaction
T_{max}	single-dose time to reach maximum (peak) concentration
TTNT	Time to next treatment
UK	United Kingdom
ULN	upper limit of the normal range
US	United States
VGPR	Very good partial remission
VTE	Venous thromboembolism
WBC	white blood cell
WHO	World Health Organization

[figure not shown]
Helsinki University Hospital Comprehensive Cancer Center Hematology
Clinical study protocol NMSG#24/15

Table 1. Schedule of study investigations

	Screening	Cycles 1- until end of study, D1 (lab within 5 days before)	Cycles 1-8, D8 D15, D22* (lab within 3 days)	Cycles 1-8 D15	Cycles 9-, D15 until end of study (lab in 3days)	End of study
Medical history	X					
Physical examination + neurool.evaluation	X	X	X**			X
Vital signs	X	X	X*		X	X
Hematology	X	X				X
Immunochemistry	X	X				X
Blood chemistry	X	X				X
Pvk+neut+tromb, K,Na,krea,alat, afos,bil (safety lab*)			X*		X	
Safety assessment, AEs	X	X	X*		X	X
BM aspiration+ 8-color EuroFlow	X		X (when VGPR has achieved, repeated if VGPR/CR and after 1 year if VGPR/CR)			
Bm-MM-FISH	X					
Bone imaging	X					
ECG (a)	X					
Thorax x-ray	X					
Cardiac ECHO	X					
Biobank	X			In CR and at relapse		
Samples to FIMM in Finland	Finland			Bm + blood at relapse		
Pregnancy test (b)	X	X (b)				
Quality of Life		X		X		X

a) ECG in C1-2, D1, thereafter if clinically needed. b) Pregnancy testing must be performed at the beginning of each 28-day cycle and at the end of study visit, applying to women of childbearing potential. * Vital signs not needed on D22 and after C2 Safety lab and AEs on D22 if clinically needed. ** Physical examination if needed due to clinical symptoms.

Table 2. Study schema

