1.5 OVERALL RISK/BENEFIT ASSESSMENT

Elotuzumab has been evaluated in several studies for RRMM patients and studies for newly diagnosed MM patients are ongoing. It has proved to have acceptable safety and efficacy combined with both lenalidomide and bortezomib. It has not

Helsinki University Hospital Comprehensive Cancer Center Hematology
Clinical study protocol NMSG#24/15

previously investigated with carfilzomib and in this study design carfilzomib has weekly dosing instead of approved twice-weekly dosing. Therefore first 5 patients will have reduced weekly dose of carfilzomib, 56 mg/m², and side effects and tolerability will be followed carefully, and in safety the following patients will have carfilzomib 70 mg/m² weekly dosing. This weekly dosing is challenging the accepted twice-weekly dosing in ARROW-study with superiority design, so the efficacy will be most probably beneficial.

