5. TREATMENT

5.1 TABLE 6. STUDY DRUG ADMINISTRATION SCHEDULE

28-day cycle, carfilzomib will be infused first

Cycles 1-2			
Agent	Dose/day	Route	Days
Carfilzomib patients 1-5	20 mg/m ²	IV	1 (cycle 1)
	56 mg/m ²	IV	8, 15 (cycle 1)
patients 1-5	56 mg/m ²	IV	1, 8, 15 (cycle 2)
Elotuzumab	10 mg/kg	IV	1, 8, 15
Dexamethasone	40 mg	Oral/IV	1, 8, 15, 22

Cycles 1-2			
Agent	Dose/day	Route	Days
Carfilzomib -patients 6-40	20 mg/m ²	IV	1 (cycle 1)
	70 mg/m ²	IV	8, 15 (cycle 1)
	70 mg/m ²	IV	1, 8, 15 (cycle 2)
Elotuzumab	10 mg/kg	IV	1, 8, 15
Dexamethasone	40 mg	Oral/IV	1, 8, 15, 22

Cycles 3-8			
Agent	Dose/day	Route	Days
Carfilzomib - patients 1-40	70 mg/m ²	IV	1, 8, 15
Elotuzumab	10 mg/kg	IV	1,15
Dexamethasone	40 mg	Oral/IV	1, 8, 15, 22

Cycles 9 – until relapse or progression			
Agent	Dose/day	Route	Days
Carfilzomib - patients 1-40	70 mg/m ²	IV	1, 15
Elotuzumab	10 mg/kg	IV	1,15
Dexamethasone	40 mg	Oral/IV	1,15

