8. DATA MONITORING COMMITTEE

The multicenter electronic Case Report Form System, where all study data will be collected and reported, is led via Principal Investigator in Helsinki University Hospital Finland. The filled data will be followed during annual meetings of Nordic Myeloma Study Group and Finnish Myeloma Group.

Independent staff of Research Units of University Hospitals in Sweden and Finland will monitor this study at level 2. Inclusion criteria, endpoints and all key test results according to the assessment schedule will be monitored to assure data quality. The investigator is required to permit direct access to the facilities where the study took place, source documents, CRFs and applicable supporting records of subject participation for audits and inspections by Ethics Committees and

Helsinki University Hospital Comprehensive Cancer Center Hematology
Clinical study protocol NMSG#24/15

National Medicines Agency. The investigator should make every effort to be available for the audits and/or inspections

The Finnish Association of Hematology will act as an external Safety Board in this study, and all adverse events will be informed and discussed every 6-8 months. Physicians who are involved in this study are not participating in the Board.

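### The safety condition on the step to carfilzomib 70 mg/m² is stated in the synopsis but not in Table 6, and no visible text ties later patients' dosing to completion of the five-patient run-in

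*Protocol*

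**What the plan says.** The synopsis (Overview of Study Design) sets carfilzomib at 56 mg/m², after a 20 mg/m² starting dose, "in the first 5 patients in the first two cycles". It continues: "If no safety problems occur the dose is increased to 70 mg/m² weekly for the rest of the study". The same sentence then sends everyone enrolled from number 6 onwards to the higher dose directly from the starting dose. Read together, these statements make the higher dose depend on what happens in the first five patients, both for those five and for everyone after them.

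Section 1.5 notes that elotuzumab has not been studied with carfilzomib and that the weekly schedule differs from the approved one. It then says: "Therefore first 5 patients will have reduced weekly dose of carfilzomib". It adds that "side effects and tolerability will be followed carefully, and in safety the following patients will have carfilzomib 70 mg/m² weekly dosing". The wording is loose, but the purpose is protective.

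Table 6 (section 5.1) is the administration schedule. The row "Carfilzomib -patients 6-40" gives 70 mg/m² from cycle 1 day 8. The rows "Carfilzomib - patients 1-40" give 70 mg/m² in cycles 3-8 and from cycle 9. No row has a condition, a footnote or an alternative if the run-in shows a problem.

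Section 8 describes an external Safety Board, with which "all adverse events will be informed and discussed every 6-8 months". It does not mention the run-in.

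**The concern.** Two parts of one protocol describe the same escalation differently: one makes it conditional, the other does not. A site that doses from Table 6 would escalate on schedule, whether or not the run-in had finished and whatever it had shown.

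This matters because section 2.1 makes safety and feasibility of the combination the primary objective, and section 10.1 says there is no information or experience with this three-drug treatment in myeloma patients. A reader of the synopsis would assume that the first five patients' experience is considered before others receive the higher dose. The visible text does not secure that.

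**Working it through.** The protocol gives no operating figure for the run-in, so there is none to reproduce. The check has two parts.

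**1. The passages side by side**

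| Item | Synopsis | Section 1.5 | Table 6 |
|---|---|---|---|
| Patients 1-5, cycles 1-2 | 20, then 56 mg/m² | 56 mg/m² | 20, then 56 mg/m² |
| Patients 1-5, cycle 3 on | 70 mg/m² if no safety problems | not stated | 70 mg/m², no condition |
| Patients 6-40 | 70 mg/m² after the starting dose, following from the same condition | 70 mg/m²; condition hinted at | 70 mg/m² from cycle 1 day 8, no condition |
| Dosing of patient 6 relative to completion of the run-in | not stated | not stated | not stated |
| Who decides | not stated | not stated | not stated |

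The one numerical safety threshold, in section 9.2 (less than 70% grade 3 or higher non-haematological events), concerns the combination as a whole and is not linked to the first five patients.

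**2. Timing**

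Inputs: 40 patients (synopsis), 24 months of recruitment (synopsis), 28-day cycles (synopsis). Uniform accrual is an assumption. A month is 365.25/12 = 30.44 days.

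- Length of the run-in for one patient: 2 × 28 = 56 days.
- Accrual rate: 40/24 = 1.67 patients per month, or one every 30.44/1.67 = 18.3 days.
- Patients starting while patient 5 completes two cycles: 1.67 × 56/30.44 = 3.07. At half the rate this is 1.5; at twice the rate, 6.1.
- With Poisson accrual at the planned rate, the probability that at least one patient starts in that time is 1 − exp(−3.07) = 95%.
- Cycle 1 day 8 falls 7 days after a patient's start. Patient 6 would therefore reach 70 mg/m² about 18 + 7 = 25 days after patient 5 starts, which is during patient 5's first cycle.
- To reach 70 mg/m² within the 56 days, a patient must start within 56 − 7 = 49 days: 1.67 × 49/30.44 = 2.7 patients (1.3 to 5.4 at half to twice the rate). Nearly all of those who start in the overlap would be escalated in it.
- Patient 9 would start 4 × 18.3 = 73 days after patient 5, so after patient 5's second cycle.
- Enrolments between Safety Board discussions: 1.67 × 6 = 10 to 1.67 × 8 = 13.

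The same spacing exposes an ambiguity within the first five. Patient 1 reaches cycle 3 on day 56, while patient 5 would start on about day 4 × 18.3 = 73. The text does not say whether the condition applies patient by patient or to the five together.

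**The case against.** The best reply is that the synopsis is part of the protocol and binds. On that reading Table 6 lists the doses planned if the condition is met; leaving out a condition stated elsewhere makes the table incomplete but does not cancel the condition. That is a fair reading, and it rules out saying that escalation would necessarily go ahead whatever the run-in showed. It does not remove the problem. Section 4 sends sites to Tables 2 and 6 for the schedule, and even the synopsis does not say whether patient 6 may be dosed before the five have finished. The content of Table 2 is not visible, so a rule shown only there would be missed.

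A reader might infer more than the documents support, in four ways:

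- *That the run-in cannot protect any later patient.* At planned accrual, patients from about number 9 (about 32 of the 35 later patients) start after patient 5's two cycles, and the synopsis condition can still apply to them.
- *That it is the only staged protection.* Section 4 makes the expansion to phase 2b depend on feasibility and safety in the 40 patients. There are also individual safeguards: overnight admission after the first combination infusion (5.2), dose-modification rules (5.2.1) and 24-hour reporting of serious adverse events (7.2). None of these is a check between patient 5 and patient 6.
- *That nobody could act within eight weeks because the Safety Board discusses events only every 6-8 months.* No text assigns the run-in decision to the Board. Sites must inform the principal investigator of severe events immediately (10.1), and the sponsor must pass on significant new safety observations without delay (7.3). What stands is that the Board's discussions are not tied to the run-in.
- *That five patients are too few to be informative.* That is a separate question about the size of the run-in and does not bear on this inconsistency.

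**Conclusion.** The point holds as an inconsistency with a practical consequence. The synopsis makes the step to 70 mg/m² conditional, section 1.5 supports that purpose, and Table 6 applies the step without condition. No visible text states the enrolment status during the run-in or names a decision-maker. The condition is thus not guaranteed to act before the first later patients are escalated.

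The exposure is a handful of patients, about 3 starting during patient 5's run-in. That count rests on uniform accrual at the planned rate, and slow early recruitment would bring it towards the lower end of the range. The inconsistency in the text does not depend on accrual. The statement that nothing else governs patient 6 is limited to the visible text. This should be corrected: the fix is specific and cheap, and the combination is one for which the protocol says there is no experience.

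**What to change.** Reconcile the synopsis, section 1.5 and Table 6 (and Table 2, if it bears on this) so that they state one rule.

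- If the condition is intended, carry it into Table 6. State whether it applies to each of the first five patients or to the five together, what the enrolment status is while the run-in is under way, and who makes the decision.
- If it is not intended, remove the conditional statement from the synopsis and align section 1.5.

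The dose, the safety criteria and the form of any hold are for the sponsor to set; this review takes no position on them. The cost is protocol wording and, if the sponsor chooses to pause enrolment, a short delay in the 24-month recruitment period.

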1. INTRODUCTION

1.1 Scientific background

Multiple myeloma (MM) is the most common hematological malignancy after lymphomas. In years 2009-2013, 955 male and 781 female new myeloma patients per year have been registered in the Nordic Cancer Registries (NORDCAN) giving an incidence of 4-6/100 000 per year (Engholm et al.2015). Multiple myeloma is considered as an incurable disease. The overall survival (OS) of patients has doubled in the last 30 years from a median of 2–3 years to 4–6 years in elderly patients, and up to 8–10 years for younger patients, due to autologous stem cell transplantation (ASCT) combined with immunomodulatory drugs and proteasome inhibitors. The International Myeloma Working Group (IMWG) recently proposed new risk stratification standards for MM patients: high-risk (HR), standard-risk (SR) and low-risk (LR) groups, t(4;14) and del(17p) indicating the worst prognosis among cytogenetic aberrations. Although a median OS of LR patients is > 10 years from diagnosis, new drugs and therapeutic innovations are urgently needed for HR patients with a median OS of only two years (Chng et al. 2014). High-dose therapy supported by ASCT is the standard first-line therapy for MM in eligible patients under 65 (-70) years.

The general consensus for induction treatment is a triple combination of proteasome inhibitor (PI) plus immunomodulatory, alkylating agent or doxorubicin with dexamethasone for 3-4 cycles. Of the second generation PIs intravenously used carfilzomib has been approved by FDA and EU for MM, and elotuzumab so far by FDA, in the setting of relapsed/refractory myeloma. All patients relapse after first-line therapy, and there may be several relapses in the course of the disease. The treatment of relapses and progression in successive treatment-lines is a challenge and has a significant impact on overall survival. In the fight against final refractoriness of the disease new and more effective drugs and their combinations are needed. Monoclonal antibody against myeloma cell together with proteasome inhibitor and/or immunomodulatory drug offers a tempting basis for an effective combination regimen.

